### 5.3 IV Medication Precautions

When administering FCM, the following precautions will be taken:

- The participant will be evaluated clinically prior to drug administration to assess the development of clinically-significant conditions.
- The vials will be visually inspected for particulate matter and discoloration before use. If noted, the vial will not be used, and the Investigator or his designee will notify the sponsor or sponsor's designee for replacement of the study drug, and for direction on the return of the unused vial.
- Heart rate and blood pressure will be assessed pre-, immediately (within 5 minutes) post, and 30 minutes post administration. Participants will be discharged from the site by the Investigator or his or her designee only if there are no significant signs or symptoms 30 minutes after the administration is completed.
- The participant will be monitored for at least 30 minutes for serious acute reactions as hypersensitivity or bioactive (labile) iron reactions to non-dextran IV iron products have rarely been reported. The reactions include: hypotension, loss of consciousness, bronchospasm with dyspnea, shortness of breath, and seizures.
  - In the event a serious acute reaction is seen, the site must have the capability to provide appropriate resuscitation measures. These may include IV NS, IV epinephrine, steroids, and/or antihistamines.

### 5.4 Drug Accountability

Investigators will keep records of the receipt, administration and return of the study drug (FCM and ferrous sulfate). They will not allow the study drug to be used for purposes other than as directed by this protocol. The investigator agrees that he/she will not supply study medication to any persons other than those enrolled in the study, or to investigators not listed on the FDA 1572. When the study is completed, or if it is prematurely terminated, a final inventory of all clinical supplies must be compiled and the remainder of the unused study drug will be returned to American Regent, Inc., or destroyed on site, per the site's documented locally accepted policies. All data regarding the study drug must be recorded as per the Monitoring Plan.

### 5.5 Concomitant Medication

All concomitant medications will be recorded in the eCRF from 30 days prior to consent. **No additional iron preparations (IV iron from 4 weeks prior to consent or oral iron**

**including multivitamins with iron, from time of consent) will be allowed. No prophylactic medications may be administered prior to FCM administration without prior approval from American Regent, Inc.**

If receiving an ESA, a stable ( $\pm 20\%$ ) dose is required for at least 8 weeks prior to consent. The ESA type, route, frequency and dose will remain unchanged throughout the study unless the dose should be decreased or held per the package label. Once decreased or held, it may not be increased or restarted unless thought necessary by the subject's physician. If the latter event occurs, these data points will be collected and the subject will continue for safety analysis.

If receiving treatment for IBD, therapy must be stable for at least 8 weeks prior to consent and remain stable through the duration of the study.

## **6.0 STUDY PROCEDURES**

### **6.1 Informed Consent**

Prior to any study specific procedures, the investigator must explain to each participant the nature of the study, its purpose, procedures to be performed, expected duration, and the benefits and risks of study participation. After this explanation, the participant (who for this trial is 1 -17 years old) must assent, if appropriate, and his/her legal guardian (who is above age of legal consent) voluntarily sign an informed consent statement (Required Elements of Informed Consent, 21 CFR 50.25). The Code of Federal Regulations (CFR) is a codification of rules and regulations of the US government. Subjects who are too young to sign an ICF, but mature enough to understand the study, will provide informed assent per local law. The subject must be able to understand that he or she can withdraw from the trial at any time and for any reason. The participant's legal guardian will be given a copy of the signed consent form.

### **6.2 Screening Phase**

#### **6.2.1 Screening Visit 1 (Day -7 $\pm$ 1)**

Each participant who qualifies for inclusion will undergo the following clinical evaluations to confirm their eligibility for the study:

- Obtain screening number from IRT
- Medical history, including documented history of an inadequate response after at least 8 weeks of prior oral iron therapy use
- Hematology, chemistries and iron indices
- Serum pregnancy test for female participants of child bearing potential (negative results must be obtained prior to randomizing the participant for study drug dosing).
- Height and weight
- Vitals signs (including sitting heart rate and blood pressure)

- Concomitant medications assessment
- ESA and IBD therapy stability (if applicable)

\*\* Participants who do not meet the entry criteria should be entered into the IRT system as a screen failure. A participant may be re-screened, only one time, once it is believed that they would qualify for study entry. The participant will need to re-sign a new consent form and all screening procedures in section 6.2 will need to be repeated.

### 6.3 Treatment Phase (Day 0 to Day 35)

#### 6.3.1 Day 0 Visit

The following will be obtained and/or completed before contacting IRT for randomization:

For all participants:

- Verify all inclusion and exclusion criteria (See section 4.2.1 and 4.2.2)
- Physical exam
- Review concomitant medications (to include ESA and IBD stability, if applicable).

A participant who develops a bacterial infection during the screening phase should be discontinued and treated appropriately. These participants may be re-screened, one time, once the enrolling physician deems the participant would qualify for study entry. The participant will need to re-sign a new consent / assent form and all screening procedures in section 6.2 will need to be repeated.

After verifying the eligibility of the participant, the IRT system will then be contacted by a study team member. Randomization will be stratified by hemoglobin (<10, ≥10 g/dL) and age (1 to <12 and ≥12 to 17 years), and randomized in a 1:1 ratio to either Group A (FCM at 15 mg/kg to a maximum single dose of 750 mg on Days 0 and 7 for a maximum total dose of 1500 mg) or Group B (Ferrous sulfate, dose and regimen dependent upon age and weight, twice daily for 28 days).

After a randomization number has been obtained, the **first dose** of oral ferrous sulfate will be administered in the clinic according to the following: infants and children (1 to <4 years of age) will receive ferrous sulfate drops; children (≥4 to <12 years of age) will receive ferrous sulfate elixir or ferrous sulfate tablets; and adolescents (≥12 to 17 years of age) will receive ferrous sulfate tablets.

A sufficient quantity of doses for a 7-day period will be dispensed to the parent or guardian of the participant. The parent or guardian of the participant will be responsible for the administration of two daily doses of oral ferrous sulfate to the participant.

After assignment of the treatment group, the following will occur:

All participant's (prior to study drug administration/dispensing, if applicable) on Day 0:

- Blood samples for central lab hematology, chemistries, and iron indices (Group

- A participants will have an additional blood sample for PK prior to dosing)
- Vital signs: temperature, sitting heart rate and blood pressure
- Weight

Group A:

- Blood samples for PK immediately (within 5 minutes) post-dose and 60 minutes post dose.
- Verify amount of single FCM dose (15mg/kg up to a maximum single dose of 750 mg).
- Administer FCM as a slow IV injection at the rate of approximately 2 mL /minute or in no more than 250 mL of normal saline and infused over 15 minutes.
- Document start and stop time of FCM administration and the total dose administered and if diluted.
- Post-administration evaluation to include measurement of sitting heart rate and blood pressure immediately (within 5 minutes) after and 30 minutes after FCM administration.
- Adverse event / serious adverse event assessment (starting at beginning of FCM injection).

Group B:

- Oral ferrous sulfate dispensing:
  - The first dose of ferrous sulfate will be administered before the end of the Day 0 visit.
  - Parents or guardians of participants will be responsible for the administration of twice daily dosing of oral ferrous sulfate. Participants that experience adverse events may continue with a dose-reduced regimen [3 mg/kg twice daily] of oral ferrous sulfate after a consult with the investigator. **(See Section 6.3.5 for oral iron dose reduction)**
  - Parents or guardians of participants will be dispensed oral iron on Days 0, 7, and 14. Used dispensing packs/blisters/syringes will be returned and are to include both the empty containers and any unused medication.
  - A record of compliance will be maintained for each participant and reviewed at each study visit. **(See Section 6.3.2 for compliance assessment)**.
  - If the participant took less than the amount of oral iron expected, document the reason(s) for missed doses and counsel the participant/parents/guardians about the importance of taking the study drug as prescribed.
- Adverse event assessment (starting once the participant takes the first in-clinic dose).

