### 5.2 Drug Administration/Regimen

The Principal Investigator or designee will supervise administration of the study drug to participants. Group B (Ferrous sulfate) the first dose of will be administered before the end of the Day 0 visit.

**Group A:** Group A (FCM) will receive a dose of FCM at 15 mg/kg to a maximum single dose of 750 mg (whichever is smaller) on Days 0 and 7 for a maximum total dose of 1500 mg. FCM will be administered as either an undiluted IV push at a rate of 100 mgs (2 mL)/minute OR in no more than 250 mL of normal saline and infused over 15 minutes.

**Group B:** Group B (Oral Ferrous sulfate) will receive an age-dependent formulation of oral ferrous sulfate daily for 28 days as follows: participants <12 years of age will receive 6 mg (elemental iron)/kg/day divided into 2 daily doses of an oral liquid formulation, either drops or elixir, and participants ≥12 will receive 2 daily doses of oral tablets. Infants and children (ages 1 to <4 years) will receive oral ferrous sulfate drops, while children (ages ≥4 to <12 years)

will have the option to receive oral ferrous sulfate elixir or oral ferrous sulfate tablets. Adolescents (ages  $\geq 12$  to 17 years) will receive an oral ferrous sulfate tablet (65 mg of elemental iron/tablet/dose) twice a day (BID). The maximum daily dose for all participants is 130 mg of elemental iron.

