### 6.3.2 Day 7 and Day 14 Visit

All participants will return to the clinic on Day 7 and 14. Prior to the administration of the study drug (if applicable), the participant will be evaluated clinically to assess for the development of clinically significant conditions that may contraindicate dosing.

- Vital signs (including sitting heart rate and blood pressure)
- Blood samples for central lab hematology, chemistries and iron indices (Group A participants will have an additional blood sample for PK prior to dosing).
- Concomitant medications assessment
- Adverse events assessment
- ESA and IBD stability (if applicable)

For Group A participants the following will be performed on **Day 7 only**:

- Blood samples for PK immediately (within 5 minutes) post-dose and 60 minutes post dose.
- Verify amount of single FCM dose (15mg/kg up to a maximum dose of 750 mg).
- Pre-administration evaluation to include measurement of heart rate, blood pressure, and body temperature.
- Administer FCM as a slow IV injection at the rate of approximately 2 mL /minute or in no more than 250 mL of normal saline and infused over 15 minutes.
- Document start and stop time of FCM administration and the total dose administered and if diluted.
- Post-administration, obtain sitting heart rate and blood pressure immediately (within 5 minutes) after and 30 minutes after FCM administration.

For Group B participants the following will be performed:

- Oral iron dispensing (**Day 7 and Day 14**).
- Compliance will be assessed according to the following:

For ferrous sulfate tablets:

- Used blister packs will be returned and are to include both the empty containers and any unused medication.
- The blister packs will be examined to assess compliance (the number taken divided by the number of pills expected to be taken). A record of compliance will be maintained for each participant and reviewed.
- If the participant took less than the number of tablets expected, document the reason(s) for missed doses and counsel the participant/parent/guardian about the importance of taking the study drug as prescribed.

For ferrous sulfate drops and elixir:

- Used oral syringes will be returned which will include any unused medication.

- The oral syringes will be examined to assess compliance (the volume remaining in the oral syringes divided by the expected amount to be taken). A record of compliance will be maintained for each participant and reviewed.

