### **6.3.5 Oral Iron Dose Reduction during the Treatment Phase**

Participants who experience adverse events possibly or probably due to the oral iron during the treatment phase will have their dose of ferrous sulfate reduced from 6 mg/kg to 3 mg/kg while maintaining the same frequency of twice per day. If the participant is receiving tablets, the dose will be reduced from one tablet taken twice daily to one tablet per day.

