### 1.3 SUMMARY OF THE STUDY DESIGN

#### 1.3.1 General Study Design and Plan

This is a Phase III, multicenter, multinational, randomized, active-controlled study that compares the efficacy and safety of FCM to oral iron in pediatric participants with IDA and a documented history of an inadequate response to oral iron therapy at least 8 weeks (56 days) prior to screening.

FCM injection is a stable, non-dextran, Type I polynuclear iron (III) -hydroxide carbohydrate complex developed as an intravenous (IV) iron replacement therapy for the treatment of IDA. The duration of this study is approximately 6 weeks and the number of sites is approximately 30. Participants who satisfy the inclusion requirements and no exclusion criteria will be eligible to participate in this study and enter into a screening phase to confirm eligibility. All eligible participants will be randomized in a 1:1 ratio to receive either FCM at 15 mg/kg to a maximum single dose of 750 mg on Days 0 and 7 for a maximum total dose of 1500 mg in Group A or oral iron (oral solution drops, elixir or oral tablets) twice daily for 28 days in Group B. Randomization will be stratified by baseline hemoglobin (<10,  $\geq$ 10 g/dL) and age (1 to <12 and  $\geq$ 12 to 17 years). The oral ferrous sulfate formulation received will be based on the participant's age, such that infants and children (1 to <4 years of age) will receive ferrous sulfate drops, children ( $\geq$ 4 to <12 years of age) will have the option to receive ferrous sulfate elixir or ferrous sulfate tablets, and adolescents ( $\geq$ 12 to 17 years of age) will receive ferrous sulfate tablets. If the participants experience adverse clinical symptoms due to the oral iron during the treatment phase, the weight-based dose of ferrous sulfate will be reduced from 6 mg/kg to 3 mg/kg. As for the participants who receive tablets, the dose will be reduced from one tablet taken twice daily to one tablet per day.

Once randomized, all participants will return for efficacy and safety evaluations, including adverse events and laboratory assessments, on Days 7, 14, 28, and 35. Additional pharmacokinetic sampling and analyses will be performed for participants receiving FCM on Days 0 and 7.

The Schedule of Events is presented by Table 1.

Table 1 Schedule of Events

Visit Day	Screening (Day -7 + 1)	Day 0	Day 7	Day 14	Day 28	DAY 35
Informed Consent / Assent	X					
Medical History	X					
Physical Exam		X				X
Inclusion/Exclusion Criteria	X	X				

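### The reduced liquid-iron dose in Protocol 6.3.1 equals the starting dose, and Protocol 6.3.2 scores liquid compliance from the volume left over

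*Protocol*

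**What the plan says.** **Dose.** Protocol 5.2 sets the liquid starting dose: "participants <12 years of age will receive 6 mg (elemental iron)/kg/day divided into 2 daily doses". It adds a ceiling: "The maximum daily dose for all participants is 130 mg of elemental iron". Section 3.2 confirms that 6 mg/kg is a total for the day. The reduction for adverse events is then described in several places:

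- Section 6.3.1 (Day 0, Group B): "Participants that experience adverse events may continue with a dose-reduced regimen [3 mg/kg twice daily] of oral ferrous sulfate", after a consult with the investigator and with a pointer to Section 6.3.5.
- Section 6.3.5: "reduced from 6 mg/kg to 3 mg/kg while maintaining the same frequency of twice per day". For tablets, "the dose will be reduced from one tablet taken twice daily to one tablet per day".
- SAP 1.3.1: "the weight-based dose of ferrous sulfate will be reduced from 6 mg/kg to 3 mg/kg". The protocol synopsis and Sections 3.1 and 4.3 give the same two figures.

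None of these statements of the reduction says whether 3 mg/kg is per day or per dose, except the 6.3.1 bracket, which makes it per dose.

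**Compliance.** Protocol 6.3.2 uses "the number taken divided by the number of pills expected to be taken" for tablets, but "the volume remaining in the oral syringes divided by the expected amount to be taken" for drops and elixir. SAP 5.1 defines reported oral-iron compliance as dose taken over dose prescribed, times 100.

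**The concern.** A dose reduction that leaves the daily dose unchanged is not a reduction. A site that follows the 6.3.1 bracket keeps a child with adverse events on the full dose. A site that follows 6.3.5, read per day, gives less. The same event in the same arm could therefore be managed differently across sites, and the prescribed dose that SAP 5.1 uses as its denominator would depend on which section the site read.

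The compliance rule raises a different problem. Liquid iron is supplied in pre-filled syringes (Section 5.1) and the used syringes come back with any unused drug, so the volume remaining is what the child did not take. A record built on that volume falls as intake rises. Tablet and liquid records within Group B would then run in opposite directions.

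**Working it through.** **1. Dose**

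Inputs: start 6 mg/kg/day in two doses, maximum 130 mg/day (Sections 3.2 and 5.2); bracket 3 mg/kg twice daily (6.3.1); reduction 6 to 3 mg/kg (6.3.5 and repeats). The documents give no weights, so those below are assumed for illustration. With w the weight in kg:

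- Start: S = min(6w, 130)
- Bracket: B = min(2 × 3w, 130) = min(6w, 130) = S
- 3 mg/kg/day: R = min(3w, 130)

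| w (kg) | S (mg/day) | B (mg/day) | R (mg/day) | B/R |
|---|---|---|---|---|
| 10 | 60 | 60 | 30 | 2.00 |
| 20 | 120 | 120 | 60 | 2.00 |
| 21.7 (= 130/6) | 130 | 130 | 65 | 2.00 |
| 30 | 130 | 130 | 90 | 1.44 |
| 40 | 130 | 130 | 120 | 1.08 |
| 43.3 (= 130/3) | 130 | 130 | 130 | 1.00 |

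B equals S in every row, so the bracket gives a 0% reduction at any weight. For comparison, tablets go from 2 × 65 = 130 to 65 mg/day.

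Which reading of 6.3.5 is intended? If its figures were per dose, the dose being reduced would be 6 × 2 = 12 mg/kg/day, which is nobody's starting dose under Section 5.2. Read per day, the starting figure matches Section 5.2 exactly, and 3 mg/kg/day is the bottom of the 3–6 mg/kg/day range in Section 3.2. In two doses that is 1.5 mg/kg twice daily.

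**2. Compliance**

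Let D be the volume dispensed, E the volume expected to be taken, and c the fraction of E taken. Assume that all unused drug is returned, so the volume remaining is D − cE.

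- Rule as written: (D − cE)/E = D/E − c
- Volume taken over expected: (D − remaining)/E = c, for any D

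| True intake c | Recorded, D = E | Recorded, D = 1.1E (assumed overage) |
|---|---|---|
| 100% | 0% | 10% |
| 90% | 10% | 20% |
| 50% | 50% | 60% |
| 0% | 100% | 110% |

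Overage shifts the scale but does not change its direction.

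**The case against.** The best defence on dose is that the intent is clear. Section 6.3.1 itself calls the regimen reduced, requires a consult and sends the reader to 6.3.5. Section 6.3.5, the synopsis, Sections 3.1 and 4.3 and SAP 1.3.1 all give 6 to 3 mg/kg, and since 6 mg/kg is a daily total, 3 mg/kg should be one too. This stands as a statement of intent. It does not cure the text: 6.3.5 omits the time unit and keeps twice-daily dosing, so a site holding the bracket can read the two sections as agreeing on 3 mg/kg per dose.

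On compliance, SAP 5.1 is correct, and the next bullet of 6.3.2 tells sites to act when a child took less than the expected volume, so the prompt for counselling points the right way. That stands too, and it limits the error to the recorded figure.

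Two stronger readings are tempting on dose. A reader might infer from the table that the 130 mg/day maximum makes the reduction defective for heavier children, because 3 mg/kg/day cuts a 30 kg child only from 130 to 90 mg/day (31%) while tablet users get 50%. The documents promise no 50% cut for liquid users and no parity with tablets, and the stated rules can be applied at every weight. Nor do they support a new 65 mg/day ceiling on the reduced dose. It would give 65/25 = 2.6 mg/kg/day at 25 kg and 65/40 = 1.6 at 40 kg, below the 3–6 mg/kg range that Appendix 1 (Amendment 1) cites for the reduction. That would be a change in comparator dosing, not a clarification.

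A reader might also infer that the bracket overdoses children. It does not: 6 mg/kg/day is the planned dose, at the top of the range in Section 3.2, and a child may stop study drug under Section 4.5.

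**Conclusion.** Both rules are wrong as written, and the severity is minor.

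- **Dose:** the 6.3.1 bracket gives a 0% reduction at every weight. Against 3 mg/kg/day it is a two-fold difference up to 21.7 kg, shrinking to none from 43.3 kg. It affects only Group B children on drops or elixir who have adverse events. How many that will be cannot be told from the documents. The conclusion about the bracket needs no assumption; the size of the gap rests on reading 6.3.5 per day.
- **Compliance:** the 6.3.2 liquid rule runs backwards. With dispensed volume equal to expected volume, 100% intake is recorded as 0%.

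A reader might infer that reported compliance or the efficacy results will be distorted. The documents do not support that: SAP 5.1 defines reported compliance from dose taken, and no analysis population or efficacy model uses compliance. The eCRF derivation is not shown, so whether the inverted figure could reach the database is open.

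**What to change.** 1. In Protocol 6.3.1, delete the bracketed dose or replace it with 1.5 mg/kg twice daily.
2. In 6.3.1, 6.3.5, the synopsis, Sections 3.1 and 4.3, and SAP 1.3.1, state the liquid reduction as from 6 mg/kg/day to 3 mg/kg/day in two divided doses. Leave the existing 130 mg/day maximum and the tablet rule as they are.
3. In 6.3.2, define drops and elixir compliance as (volume dispensed − volume remaining) / expected volume, in line with the tablet rule and SAP 5.1.
4. Check that the eCRF derives liquid compliance and dose taken from volume taken.

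The cost is a wording correction, a note to sites and a check of one derivation, with no added visits, procedures or participants. Section 9.8.5 allows clarifications by numbered memo. If the sponsor judges that the dose wording affects participant welfare, Section 9.8.4 requires an amendment with IRB approval, and the change can go into the next one.
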